9.7.3.5 Clinical Pregnancy

Clinical pregnancy is defined as a TVUS showing at least 1 intrauterine gestational sac with fetal heart beat at 6 and 10 weeks post-oocyte retrieval. The frequency and proportion of subjects that are clinically pregnant at 6 and 10 weeks post-oocyte retrieval will be derived for subjects in the mITT and safety cohorts for subjects that had oocyte(s) retrieved. Associated 95% confidence intervals for these event rate estimates will also be presented.

For the clinical pregnancy rate derivation at 6 weeks post-oocyte retrieval, if a subject has missing TVUS assessment and no other TVUS assessment at a later date, the subject will be counted as not having a clinical pregnancy. In contrast, if there is a later assessment with at least 1 intrauterine gestational sac with fetal heart beat, the subject will be imputed as having a clinical pregnancy at 6 weeks post-oocyte retrieval.

9.7.4 Other Assessments

9.7.4.1 Number and Size of Follicles during Stimulation

For each subject, the number of follicles on stimulation day 1 and last day of stimulation will be summarized for the mITT and ES cohorts. The summary will include the following:

1. the number of subjects that have follicles of size <10 mm, 10 mm, 11 mm, 12 mm, 13 mm, 14 mm, 15 mm, 16 mm, and ≥ 17 mm,
2. a summary of the number of follicles ≥ 17 mm (the count for each subject will be summarized across subjects),
3. the number of subjects that have at least two follicles that are ≥ 17 mm, and

4. a summary of the percentage of follicles ≥ 17 mm, ≥ 15 mm, and ≥ 12 mm (for each subject the percentage will be first derived and this subject level summary will be summarized across subject using mean, SD, etc.).

9.7.4.2 E2 and Progesterone Profiles

The central laboratory E2 and progesterone profiles will be summarized for mITT and ES cohorts, using descriptive statistics by scheduled visit, as well as for the change from screening for post-screening visits.

For patients in the mITT population, the local laboratory E2 assessments will be summarized by visit.

9.7.4.3 Oocytes

For each subject, the number of oocytes retrieved, the number of germinal vesicle, metaphase I, metaphase II and Degenerated oocytes will be summarized by frequency distribution and by descriptive statistics for the mITT and ES cohorts.

9.7.4.4 Characterization of Fertilized Oocytes one Day (Day 1) after Oocyte Retrieval

The status of fertilized oocytes will be summarized 1 day after oocyte retrieval for the mITT and ES cohorts. The summary will be both at the subject level and at the oocyte level.

For the summary at the subject level, for each subject, the percentage of fertilized oocytes with pronuclei 2 pn will be derived. The percentage will be derived over the number of oocytes retrieved. These percentage will further be summarized using descriptive statistics (i.e., mean, SD, etc.). The percentage of fertilized oocytes with continue destiny will be similarly analyzed.

For the fertilized oocyte level summary, the number and percentage of fertilized oocytes falling in each category of pronuclei will be presented (i.e., >2 pn, 2 pn, 1 pn, 0 pn and damaged). The percentage derivation will be over the total number of oocytes classified.

These summaries will be obtained for mITT and ES cohorts.

9.7.4.5 Quality of Blastocysts 5 Days (Day 5) after Oocyte Retrieval

The quality of blastocysts 5 days after oocyte retrieval will be assessed at both the blastocyst level and at the subject level. The evaluation of fertilized oocytes at Day 5 will consist of assessment of embryo stage and classification of blastocysts according to blastocyst expansion and hatching status, blastocyst inner cell mass grading and trophectoderm grading. Furthermore, the destiny of the embryo will be recorded.

Embryo stage is classified as blastocyst, morula, degenerated or cleavage stage. For embryos still at the cleavage stage the number of blastomeres will be recorded.

Destiny at Day 5 is either transferred, cryopreserved or out of trial.

The scoring of blastocysts is based on the classification system by Gardner & Schoolcraft ([Gardner, 1999](#)).

Blastocyst expansion and hatching status will be assessed as one of the following:

1. An early blastocyst, blastocoel being less than half volume of that of the embryo
2. A blastocyst with a blastocoel whose volume is half of, or greater than half of, that of the embryo
3. A blastocyst with a blastocoel completely filling the embryo
4. An expanded blastocyst with a blastocoel volume larger than that of the early embryo, with a thinning zona
5. A hatching blastocyst with the trophectoderm starting to herniate through the zona
6. A hatched blastocyst, in which the blastocyst has completely escaped from the zona

For blastocysts with expansion and hatching status on Day 5, blastocyst inner cell mass grading and trophectoderm grading will be evaluated.

Blastocyst inner cell mass grading will be assessed as one of the following:

- A. Tightly packed, many cells
- B. Loosely grouped, several cells
- C. Very few cells

Trophectoderm grading will be assessed as one of the following:

- A. Many cells forming a cohesive epithelium
- B. Few cells forming a loose epithelium
- C. Very few, large cells

Based on the blastocyst expansion and hatching status, blastocyst inner cell mass grading and trophectoderm grading, the embryo will be classified as a good-quality blastocyst if the grade is 3BB or above as illustrated in [Table 9-2](#).

Table 9-2 Good-Quality Blastocysts

3AA	4AA	5AA	6AA
3AB	4AB	5AB	6AB
3AC	4AC	5AC	6AC
3BA	4BA	5BA	6BA
3BB	4BB	5BB	6BB
	4BC	5BC	6BC
	4CA	5CA	6CA
	4CB	5CB	6CB
	4CC	5CC	6CC

The embryos on Day 5 will be summarised on both the embryo level and at the subject level.

Embryo Level

At the embryo level all embryos evaluated will be included in the tables when reporting embryo stage and destiny of the embryo. For summary of blastocyst expansion and hatching status, blastocyst inner cell mass grading and trophectoderm grading all available embryo evaluations will be included. Frequency tables will be produced for the embryo stage, destiny, blastocyst expansion and hatching status, blastocyst inner cell mass grading and trophectoderm grading. These summaries will be obtained for the subjects in the mITT and ES cohorts.

Subject Level

At the subject level the following will be derived for all subjects in the mITT and ES cohorts for the subjects that had oocytes retrieved:

- Number of blastocysts at Day 5
- Number of good-quality blastocysts at Day 5

These counts will be summarized using descriptive statistics of mean, median, SD, minimum and maximum.

9.7.4.6 Endometrial Thickness

Endometrial thickness at the time of blastocyst transfer will be summarized for the mITT and ES cohorts.

9.8 Extent of Exposure and Treatment Compliance

9.8.1 PVR

The total number of PVRs used and the duration of treatment will be summarized. The total number of subjects who prematurely discontinued PVR and the associated reasons for discontinuation will also be summarized. Furthermore, the drug compliance rate will also be summarized for the mITT and safety cohorts. Compliance is defined as follows:

(number of PVRs used)/ (number of PVRs expected to be used).

These summaries will be generated for the safety cohort. Additional information collected in the drug accountability eCRF module may be summarized. A detailed associated listing will be produced.

9.8.2 Oral Contraceptives

The type of oral contraceptives used and the duration of treatment will be summarized for the ES and safety cohorts.

9.8.3 MENOPUR, Leuprolide Acetate, and hCG

The total dose of MENOPUR and leuprolide acetate administered and the duration of treatment will be summarized for the ES and safety cohorts. The number of subjects that receive hCG will also be summarized for the ES and safety cohorts.

9.9 Safety

9.9.1 General Considerations

Safety parameters will be evaluated for the ES and safety cohorts. Safety summaries will be presented by the 5 phases of the trial. These phases are defined as follows:

- Screening Phase: From the date of signing the informed consent through the day before the start of the oral contraceptive treatment.
- Suppression Phase: From the start of oral contraceptive treatment until the day before the start of the stimulation phase (start of MENOPUR treatment).
- Stimulation Phase: From the date of the first dose of MENOPUR through the day before the start of IMP.
- Treatment Phase: From the date of the first dose of IMP (PVR) through the end of the trial.
- Study Phase: From the date of the first dose of oral contraceptive through the end of the trial.

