There are 3 analysis cohorts for this trial. The mITT cohort consists of all subjects who had successful oocyte retrieval, received at least 1 dose of IMP, and had completed fresh embryo transfer. The safety cohort comprises all subjects treated with IMP. The eligible subjects (ES) cohort consists of all subjects who were deemed eligible for trial participation based on inclusion and exclusion criteria at screening and treated with oral contraceptives, leuprolide acetate, or MENOPUR.

The primary objective is to estimate the cumulative rate of any spontaneous abortion, including spontaneous clinically recognized pregnancy loss and blighted ovum during the trial (up to Week 12 following oocyte retrieval) for subjects in the mITT cohort. The number and rates of any spontaneous abortions will be summarized and associated exact 95% confidence intervals will be generated. Furthermore, as part of a Bayesian sensitivity analysis, a 95% credible interval will be generated. The spontaneous abortion rate, biochemical abortion rate, clinical pregnancy rate, and positive β -hCG rate will be similarly analyzed for the mITT and safety cohort, for subjects that had oocyte(s) retrieved. However, for these endpoints, credible intervals will not be derived. Furthermore, safety will be assessed by summarizing treatment-emergent AEs for the safety and ES cohorts. Treatment-emergent AEs will be summarized overall, by grade (intensity), seriousness, and drug relatedness by system organ class and preferred term using the Medical Dictionary for Regulatory Activities. A treatment-emergent AE is any AE that occurs after the start of PVR and through the end of the trial, or a pretreatment AE/medical condition that worsens in intensity after the start of PVR. Furthermore, a separate treatment-emergent AE summary table will be generated for AEs of special interest, such as vaginal pain and irritation, vaginal infection, vaginal bleeding/spotting, vaginal hemorrhage, vaginal adhesions and vaginal or cervical abrasions and lesions. These events will also be further analyzed by grade (intensity). Tolerability for the safety cohort will be assessed by summarizing the total number of subjects who prematurely discontinued PVR and the associated reasons for discontinuation. This summary will be based on the safety cohort.

For the safety and ES cohorts, the number of subjects with abnormal clinical laboratory and vital sign assessments will be summarized.

TABLE OF CONTENTS

SYNOPSIS.....	2

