6.3 Treatment with PVR

6.3.1 Visit 4: Initiation of Treatment with PVR

Treatment with PVR will be initiated one day after oocyte retrieval (Visit 4).

The following must take place at the visit:

- Vital signs
- Blood collection for assessment of:
 - Clinical chemistry and hematology parameters (*Note:* if Visit 4 occurs on a day where shipment to the central laboratory is not feasible, e.g. during the weekend, the subject will return to the site for blood collection on the next possible day)
 - Endocrine parameters (progesterone and estradiol)
- Assessment of vaginal hemorrhage
- Pelvic examination (documentation of presence and grade [intensity] of any pain, irritation, abrasions, or lesions on the cervix or vagina or vaginal adhesions, see [Appendix 2](#)).
- Dispensing of IMP: the first 4 PVRs will be distributed (PVR1, PVR2, PVR3 and PVR4). Subjects will be instructed in the proper method for PVR insertion and removal (see [Appendix 1](#)). The subject will insert PVR1 while at the trial site. Subjects will be allowed to remove the

PVR for up to 1 hour/day; this includes removal for sexual intercourse, although this is not necessary.

- Provide subjects with PVR diary and instructions on how to complete the diary. Subjects will be asked to fill out the diary at home for each PVR used and bring it to each subsequent visit.
- Provide subjects with bleeding log and instructions as to how to differentiate between vaginal discharge and bleeding (to capture the frequency and intensity of any bleeding). Subjects will be asked to fill in the bleeding log at home and bring it to each subsequent visit.
- Provide subjects with sanitary napkins. Subjects will be instructed to use only sanitary napkins provided by the trial site for any bleeding that occurs during the trial.
- Recording of use of any concomitant medication
- Recording of AEs

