7.2.5 Vaginal Hemorrhage

The presence or absence of vaginal haemorrhage as defined in section [8.3.6](#) will be assessed by the Investigator at all visits starting at Visit 4 where the first distribution of PVR takes place.

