8.2.2 Recording of Adverse Events

The Investigator must record all AEs in the AE Log provided in each subject's eCRF with information about:

- AE description
- Date and time of onset (time can be omitted, if not applicable)
- Intensity
- Causal relationship to IMP
- Action taken to IMP
- Other action taken
- Date and time of outcome (time can be omitted, if not applicable)
- Outcome
- Seriousness.

Each of the items in the AE Log is described in detail in the following sections.

Adverse Event

AEs should be recorded as diagnoses, if available. If not, separate signs and symptoms should be recorded. One diagnosis/symptom should be entered per record.

If a subject suffers from the same AE more than once and the subject recovers in between the events, the AEs should be recorded separately. If an AE changes in intensity, a worst-case approach should be used when recording the event, i.e., the highest intensity and the longest duration of the event.¹

Note the following: a procedure is not an AE; the reason for conducting the procedure is. Hospitalization is not an AE; the reason for hospitalization is. Death is not an AE, but the cause of death is (an exception is sudden death of unknown cause, which is an AE).

¹ Exception: if an AE with onset before the first IMP administration (i.e., a pretreatment AE) worsens in intensity, this must be recorded as 2 separate events. The initial AE should be recorded with outcome "not recovered" and the date and time of outcome are when the intensity changed. The second AE should be recorded with date and time of onset when the intensity changed.

Date and Time of Onset

The date of onset is the date when the first sign(s) or symptom(s) were first noted. If the AE is an abnormal clinically significant laboratory test or outcome of an examination, the onset date is the date the sample was taken or the examination was performed.

Intensity

The intensity of an AE must be classified using the following 3-point scale:

Mild: Awareness of signs or symptoms, but no disruption of usual activity.

Moderate: Event sufficient to affect usual activity (disturbing).

Severe: Inability to work or perform usual activities (unacceptable).

The grading of AEs of special interest will be based on predefined criteria as discussed in section [8.3](#).

Causal Relationship to IMP

The possibility of whether the IMP caused the AE must be classified as one of the following:

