### 10.2 Adverse Events

Adverse events (AEs) are classified according to the latest available version of Medical Dictionary for Regulatory Activities (MedDRA).

Written narratives will be issued for all serious AEs (including deaths). Treatment-emergent AEs are AEs that occur during the *treatment phase* or a pre-existing medical condition that worsened in intensity during the *treatment phase*.

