#### **10.4.2 Vaginal Hemorrhage**

Vaginal hemorrhage is defined in [Section 8.3.6](#) of the protocol and the assessment of vaginal hemorrhage will be collected in a specific eCRF module. Based on the eCRF module, the number of subjects with vaginal hemorrhage will be summarized for the Safety cohort.

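### Treatment-emergent status turns on the calendar date of the first ring, so a pelvic finding seen at Visit 4 before insertion counts if it is reported as an AE

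*Protocol*

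**What the plan says.** **Phases.** Protocol 9.9.1 gives "Treatment Phase: From the date of the first dose of IMP (PVR) through the end of the trial". The phase before it is "Stimulation Phase: From the date of the first dose of MENOPUR through the day before the start of IMP". SAP 1.1.1 and 10.1 carry the same definitions. The whole of the first-ring day therefore belongs to the treatment phase.

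**Treatment-emergent.** Protocol 9.9.2 and SAP 10.2 count every AE in the treatment phase, and also "a pre-existing medical condition that worsened in intensity during the" treatment phase. The synopsis words it differently: "A treatment-emergent AE is any AE that occurs after the start of PVR".

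**Visit 4.** Protocol 6.3.1 places the first ring one day after retrieval. Its list for that visit puts the hemorrhage assessment and the pelvic examination ahead of dispensing and inserting PVR1. Retrieval itself is done under transvaginal ultrasound guidance (6.2.3).

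**Dating and reporting.** For an examination finding recorded as an AE, Protocol 8.2.2 says "the onset date is the date the sample was taken or the examination was performed". Time of onset may be left out. Protocol 7.2.8 makes any clinically significant pelvic finding an AE, and 8.1 exempts only conditions diagnosed at screening. The note to Appendix 2 instead ties AE reporting of pelvic findings to the period after treatment has begun.

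**Tables.** The special-interest table (Protocol 9.9.2.1, SAP 10.2.3) is split by preferred term, grade and seriousness. The pelvic shift table (Protocol 9.9.7, SAP 10.4.3) starts from Visit 4. Hemorrhage is assessed "at all visits starting at Visit 4 where the first distribution of PVR takes place", and in SAP 10.4.2 "the number of subjects with vaginal hemorrhage will be summarized for the Safety cohort".

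**The concern.** Local tolerability of the ring is one of the things this single-arm safety trial is designed to describe, and abrasions, lesions, pain and bleeding are secondary endpoints. Vaginal or cervical abrasions and lesions at screening are an exclusion (criterion 22). A lesion first seen at Visit 4 before insertion therefore arose between screening and Visit 4, an interval that contains the retrieval. Such a finding cannot reflect ring exposure, yet the date rule can place it in the treatment-emergent and special-interest tables. There is no control arm against which to read a procedural background rate.

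The rule also makes the outputs inconsistent. The same Visit 4 examination is the starting point of the shift table and an on-treatment observation in the AE table. SAP 10.3 and 10.3.5 take Visit 4 as baseline for laboratory values and vital signs. SAP section 12, which lists differences from the protocol, does not mention that the synopsis defines treatment-emergent differently.

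**Working it through.** The documents give no figure on this point, so the check is one of dates. Take the retrieval day as day 0. Protocol Table 6-1 and 6.3.1 then put Visit 4, and so the first ring, on day 1. The rule in Protocol 9.9.1 is: treatment phase if onset date ≥ date of first ring.

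| Event | Onset date | Date rule (9.9.1, SAP 10.1) | Synopsis rule |
|---|---|---|---|
| Sign or symptom first noted on retrieval day | day 0 | 0 < 1: stimulation phase, treatment-emergent only if it worsens | before the ring: same result |
| Finding at Visit 4 examination, before insertion, reported as an AE | day 1 (examination date) | 1 ≥ 1: treatment-emergent | before the ring: not treatment-emergent unless it worsens |
| Event on day 1 after insertion | day 1 | treatment-emergent | treatment-emergent |

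Only the middle row differs. For that row:

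1. **Is it an AE?** Yes under Protocol 7.2.8 and 8.1 if clinically significant. Not under the Appendix 2 note, because treatment has not begun. The two texts conflict, so sites may report differently.
2. **Is it pretreatment?** The footnote in Protocol 8.2.2 defines a pretreatment AE by onset before the first IMP administration, so by that text it is. By the date rule it is not.
3. **What if it later worsens?** The footnote requires two records. Under the date rule both are treatment-emergent (2 events). Under the synopsis rule only the worsening is (1 event).
4. **Does it reach the special-interest table?** Yes, if it is coded to one of the preferred terms in SAP Appendix 3. No causality split is named for that table.

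**Size.** The documents give no rate of reportable pre-insertion findings, so the rates below are assumptions. The special-interest table uses the safety cohort, meaning all women treated with the ring. Its size is not stated, so 240 (the mITT target) stands in for it. Women affected = rate × 240:

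- 1%: 0.01 × 240 = 2.4, about 2
- 2%: 0.02 × 240 = 4.8, about 5
- 5%: 0.05 × 240 = 12
- 10%: 0.10 × 240 = 24

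The 5% incidence tables need 0.05 × 240 = 12 women. Twelve such findings under one preferred term would reach that threshold with no event after insertion.

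**The case against.** The other side has a good deal of force.

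- **Not every text counts these findings.** The Appendix 2 note, the 8.2.2 footnote and the synopsis all lean towards leaving them out. This stands: the documents conflict.
- **Treatment-emergent does not mean related.** A reader might infer that retrieval trauma is attributed to the ring. The documents do not support that. Causality is assessed for each AE (8.2.2), treatment-emergent AEs are tabulated by causality (9.9.2), and relatedness is part of the abrasion, lesion and adhesion endpoint (2.2). What remains is that the special-interest table itself shows no split.
- **The finding stays visible.** Pelvic grades are summarized by visit and shifted from Visit 4, so a retrieval finding appears there as a Visit 4 value. This stands, but it does not correct the AE counts.
- **The order of procedures is inferred.** Protocol 6.3.1 lists what must happen at the visit and does not say that the examination comes first. The list order and the shift table imply it.
- **Hemorrhage is a weaker case.** That count is not labelled treatment-emergent, and the hemoglobin criterion in 8.3.6 is already restricted to post-treatment values. Only the blood-loss and transfusion criteria could admit a pre-insertion entry.
- **A date cut-off is workable and errs towards over-counting.** The PVR diary (7.3.6) and the required source data (10.1) call for dates of ring use and specify no insertion time, so a rule by clock time could not be relied on. That rules out a date-and-time definition. It does not rule out classifying the finding by the examination at which it was made.

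**Conclusion.** The point holds in a limited form. Under Protocol 9.9.1–9.9.2 and SAP 1.1.1, 10.1 and 10.2, a clinically significant finding first seen at the Visit 4 pelvic examination before PVR1 is inserted is treatment-emergent if it is reported as an AE. It can then enter a special-interest table that has no causality split. This contradicts the synopsis and the 8.2.2 footnote, and it sits badly with Visit 4 as the start of the shift table.

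A reader might go further and infer that retrieval effects in general are counted against the ring. The dates do not bear this out: symptoms first noted on the retrieval day fall in the stimulation phase, and findings not reported as AEs go only to the by-visit and shift summaries.

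The number of women affected is unknown. The range of about 2 to 24 rests wholly on assumed rates and on 240 as the denominator, and the conclusion assumes that the examination precedes insertion. The primary endpoint is unaffected, because it is derived from β-hCG tests, ultrasound and pregnancy-loss AEs and does not use treatment-emergent status. The mismatch is worth correcting because a stated rule produces it and it can be removed cheaply.

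**What to change.** 1. Align Protocol 9.9.1–9.9.2 and SAP 1.1.1, 10.1 and 10.2 with the synopsis, so that treatment-emergent means onset after the ring has been started.
2. Classify AEs that match findings recorded at the pre-insertion Visit 4 pelvic examination as pretreatment (stimulation phase), and count them as treatment-emergent only if they later worsen. Keep every other same-day event of unknown timing as treatment-emergent, so that uncertain cases still count.
3. In the SAP 10.4.2 count, show hemorrhage entries from the pre-insertion Visit 4 assessment separately.
4. State in Protocol 6.3.1 that the Visit 4 examination precedes insertion, as the list order and the shift table already imply.
5. Reconcile 7.2.8 and 8.1 with the Appendix 2 note, so that all sites report pre-insertion findings in the same way.

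The cost is small: wording in both documents, some programming, and a check of AEs dated on the Visit 4 day against the pelvic examination and hemorrhage eCRF pages. No insertion time has to be collected, and neither the sample size nor the primary analysis changes.
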